#### **4.1.1 Dose Escalation**

In the Dose Escalation of GEN3014, there are 2 disease cohorts:

- **RRMM Cohort:** (See Sections 5.1.1 and 5.2.1 for Inclusion and Exclusion criteria.) GEN3014 will be tested in RRMM subjects at 6 DLs. In addition to subjects whose prior lines of therapy included an anti-CD38 mAb (ie, daratumumab, isatuximab), anti-CD38 mAb-naïve subjects with RRMM are allowed to be enrolled.
- **R/R AML Cohort:** (See Sections 5.1.1 and 5.2.1 for Inclusion and Exclusion criteria.) GEN3014 will be tested in R/R AML at 3 DLs. The R/R AML Cohort will be initiated after the trial has cleared the DL of 16 mg/kg in the RRMM Cohort with preliminary data on safety, PK, and pharmacodynamics in subjects with RRMM who have been treated with GEN3014 at DLs up to 16 mg/kg (see Section 4.3.1.2). Based on emerging data in subjects with R/R AML treated with GEN3014, DLs for R/R AML including intermediate doses may be adjusted accordingly during the course of the trial.

Rationales for the starting dose and dosing regimen for each disease indication are provided in Section 4.3.1.

Safety assessments will be performed as indicated in Table 1-1 (subjects with RRMM) and Table 1-2 (subjects with R/R AML).

At each DL, DLTs will be assessed in the first treatment cycle, ie, a DLT evaluation period of 28 days from Cycle 1 Day 1. The RP2D and MTD (if reached) for RRMM and R/R AML will be determined.

For all subjects, in Cycle 1 the first dose of GEN3014 will be split into 2 doses and administered on 2 consecutive days, ie, Cycle 1 Day 1 and Cycle 1 Day 2. All doses will be administered based on the subject's current weight.

#### **Subjects with RRMM**

Subjects with RRMM will be enrolled at the trial initiation and dosed according to the schedule shown in Table 4-1.

**Table 4-1 GEN3014 Dose Administration – Subjects with RRMM (Dose Escalation)**

Subjects with MM	Minimum Number of Subjects	Dose Level	Dose Administered in Cycle 1	Dose Administered Each Dosing Day, Cycle 2 and Beyond
MM-DL1	1	0.2 to 0.6 mg/kg (intrasubject dose escalation)	Days 1 and 2: 0.1 mg/kg/day	0.6 mg/kg
			Days 8 and 9: 0.3 mg/kg/day	
			Day 15: 0.6 mg/kg	
			Day 22: 0.6 mg/kg	
MM-DL2	1	2 mg/kg	Days 1 and 2: 1 mg/kg/day	2 mg/kg
			Day 8: 2 mg/kg	
			Day 15: 2 mg/kg	
			Day 22: 2 mg/kg	
MM-DL3	3	4 mg/kg	Days 1 and 2: 2 mg/kg/day	4 mg/kg
			Day 8: 4 mg/kg	
			Day 15: 4 mg/kg	
			Day 22: 4 mg/kg	
MM-DL4	3	8 mg/kg	Days 1 and 2: 4 mg/kg/day	8 mg/kg
			Day 8: 8 mg/kg	
			Day 15: 8 mg/kg	
			Day 22: 8 mg/kg	
MM-DL5	3	16 mg/kg	Days 1 and 2: 8 mg/kg/day	16 mg/kg
			Day 8: 16 mg/kg	
			Day 15: 16 mg/kg	
			Day 22: 16 mg/kg	
MM-DL 6	3	24 mg/kg	Days 1 and 2: 12 mg/kg/day	24 mg/kg
			Day 8: 24 mg/kg	
			Day 15: 24 mg/kg	
			Day 22: 24 mg/kg	

**Note:** For MM-DL1, split doses are administered on Days 1-2 and Days 8-9 of Cycle 1; full doses are administered on subsequent dosing days. For all other MM-DL cohorts, split doses are administered only on Days 1-2 of Cycle 1; full doses are administered on subsequent dosing days.

Additional DL such as 20 mg/kg or modified dosing schedule(s) may also be explored based upon emerging data.

DL=dose level; RRMM=relapsed or refractory multiple myeloma; MM=multiple myeloma.

For the intrasubject dose escalations at MM-DL1 during Cycle 1 (DLT period; see Section 4.3.1), in order to be escalated to a higher dose, the subject must have tolerated the lower dose and must not have experienced any GEN3014-related toxicity of CTCAE grade  $\geq 2$  excluding grade 2 IRR at the lower dose originally assigned.

In the RRMM Cohort, the initial 2 MM-DLs will enroll 1 subject each (ie, accelerated titration). The trigger point to expand a 1-subject DL into a 3-subject DL (eg, adding 2 subjects to a single-subject cohort) is the observation of any of the following events during the first 28 days of treatment (ie, Cycle 1):

- Any hematologic toxicity  $\geq$  grade 2.
- Any non-hematologic toxicity but not classified as an IRR  $\geq$  grade 2.
- Any IRR  $\geq$  grade 3.
- A DLT (see Section 6.6.1) is observed at any time within the first 28 days (Cycle 1).

AEs of specified grades, regardless of relationship to GEN3014, should be considered relevant for transitioning from single subject into the standard 3 subjects at the initial 2 DLs (single-subject DLs), unless the event can clearly be determined to be unrelated to the drug. All of the AEs of specified grades should be classified as DLTs except those that are clearly and incontrovertibly due to the underlying disease or extraneous causes.

If not earlier, when initiating MM-DL3, the sample size will default to 3.

If any single-subject MM-DL is expanded to a total of 3 subjects (based on a trigger point above being reached), all subsequent MM-DL(s) will have 3 subjects. When all subjects at the first 3-subject DL have completed the DLT period, the mBOIN algorithm (see Section 4.1.2) will suggest the next DL.

If expanding from a single-subject to 3 subjects on MM-DL1, where intrasubject dose escalation is applied during Cycle 1, the same intrasubject dose escalation is applied to the additional subjects. The same principle applies if MM-DL1 would be revisited at a later stage (eg, if de-escalation from MM-DL2 to MM-DL1 would be recommended; see Section 4.1.2 for further details on escalation rules).

Additional DLs, including an intermediate dose(s) (eg, 20 mg/kg) or modified dosing schedule(s) may also be explored based upon emerging data.

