#### **4.1.2.3 Dose Escalation Cohort Size**

In the standard titration with 3 subjects per cohort, a recommendation based on Table 4-3 may be made in the following scenario: if 1 out of the 3 initial subjects on a new DL is non-DLT

evaluable and the remaining 2 are DLT-evaluable; provided that neither of the 2 subjects experienced any grade  $\geq 2$  non-hematologic toxicity excluding grade  $\leq 2$  IRRs, nor any DLT during the 28-day DLT period. (See Section 9.3 for a definition of DLT-evaluable.) In this example the BOIN would recommend an escalation. (It is not necessary to replace the non-DLT evaluable subject to proceed with the escalation.)

Also, over-recruitment by 1 subject is allowed, so that each 3-subject cohort may consist of 2 to 4 subjects who are evaluable for DLT.

In case a cohort had less than 3 DLT evaluable subjects, the next cohort on the same DL may be enlarged to bring the number of subjects on the DL up to a multiple of 3.

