## 6.6 Dose Modifications

### 6.6.1 Dose-Limiting Toxicity (Dose Escalation)

The DLT Evaluation Period is defined as the first 28 days of GEN3014 treatment (ie, Cycle 1). Toxicities will be graded for severity according to the National Cancer Institute Common Terminology Criteria for Adverse Events (NCI-CTCAE), v5.0, with the exception of TLS (see Section 10.3.7).

The occurrence of any of the toxicities outlined in this section will be considered a DLT.

- All Grade 5 toxicities
- Hematological toxicities listed below:
  - Grade 4 thrombocytopenia (platelet count  $<25.0 \times 10^9/L$  [ $<25,000/\mu L$ ]) lasting  $>7$  consecutive days not attributable to the underlying disease.
  - Grade 4 neutropenia (neutrophil count  $<0.5 \times 10^9$  cells/L [ $<500/\mu L$ ]) lasting  $>7$  consecutive days not attributable to the underlying disease.
  - Grade 3 and grade 4 febrile neutropenia (neutrophil count  $<1.0 \times 10^9$  cells/L with a single temperature of  $>38.3^\circ C$  [ $100.9^\circ F$ ] or with a sustained temperature of  $\geq 38^\circ C$  [ $\geq 100.4^\circ F$ ] for more than 1 hour) lasting  $>2$  days.
  - Grade 3 and grade 4 hemorrhage associated with thrombocytopenia of  $\geq$  grade 3 requiring platelet transfusion.
  - Grade 4 anemia
- Note: Since bone marrow aplasia is an expected consequence of AML therapies, only persistent pancytopenia lasting  $\geq 14$  days and not related to leukemia infiltration will be considered as a DLT for the R/R AML Cohort. Bone marrow evaluation may be required to determine if marrow aplasia is due to leukemia.
- Non-hematological toxicities:
  - All non-hematological toxicities of grade  $\geq 3$  (severe or life-threatening), **excluding** the following:
    - a. Grade 3 fever ( $>40.0^\circ C$  [ $>104.0^\circ F$ ]) for  $\leq 24$  hours
    - b. Grade 3 hypotension (medical intervention indicated; hospitalization indicated) resolving in  $\leq 24$  hours
    - c. Laboratory values out of normal range that do not have any clinical consequence, are clinically transient in nature and that resolve in  $\leq 3$  days (including electrolyte abnormalities that respond to medical intervention)
    - d. Grade 3 AST and/or grade 3 ALT returning to grade 1 or baseline in  $\leq 7$  days
    - e. Grade 3 nausea that responds to adequate antiemetic treatment in  $\leq 3$  days
    - f. Grade 3 vomiting that responds to adequate antiemetic treatment in  $\leq 3$  days

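### One sentence in Protocol 4.1.1 classifies the cohort-expansion triggers at MM-DL1 and MM-DL2 as DLTs, contrary to the definition in 6.6.1

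*Protocol*

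**What the plan says.** **Protocol 4.1.1, Subjects with RRMM.** MM-DL1 and MM-DL2 open with one subject each. Four kinds of Cycle 1 event trigger the addition of two more:

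- haematologic toxicity of grade 2 or more;
- "Any non-hematologic toxicity but not classified as an IRR", at grade 2 or more;
- an IRR of grade 3 or more;
- "A DLT (see Section 6.6.1) is observed at any time within the first 28 days (Cycle 1").

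The paragraph after the list says that AEs of the specified grades matter for the move from one to three subjects unless clearly unrelated to the drug. The next sentence reads: "All of the AEs of specified grades should be classified as DLTs except those that are clearly and incontrovertibly due". The exception covers events explained by the malignancy itself or by outside factors.

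**Protocol 6.6.1.** "The occurrence of any of the toxicities outlined in this section will be considered a DLT". Grade 4 neutropenia and grade 4 thrombocytopenia count only if they last more than 7 consecutive days, febrile neutropenia only if it lasts more than 2 days, and anaemia only at grade 4. "All non-hematological toxicities of grade" 3 or more count, apart from listed exclusions such as "Grade 3 nausea that responds to adequate antiemetic treatment in" 3 days or less. A separate criterion covers raised ALT or AST together with raised bilirubin. The section applies its criteria to every AE in the DLT evaluation period and makes no exception for the single-subject levels. Its Note carries the same classification sentence as 4.1.1.

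**SAP.** Section 5.3 names DLTs as a primary endpoint of Dose Escalation, presented on the DDS. Under Section 4.5 a subject enters the DDS by receiving 4 of 4 planned Cycle 1 doses with sufficient safety evaluations, or by having a DLT. Sections 4.5, 5.3 and 5.5.2.2 use the term without defining it.

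**The concern.** The protocol gives two answers to whether a given event at MM-DL1 or MM-DL2 is a DLT, and the answer depends on which section is opened. In 4.1.1 the phrase about specified grades occurs in two consecutive sentences. In the first it clearly means the expansion triggers, so in the second it turns those triggers into DLTs.

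DLT incidence is a primary endpoint of Dose Escalation, and a DLT is also a route into the DDS. The definition can therefore move both the numerator and the denominator of the reported count. The SAP does not settle it. Its Section 1.2 refers the reader to the protocol for further design detail, and the protocol contains both texts.

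**Working it through.** **Step 1: the two texts side by side.**

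| Event at MM-DL1 or MM-DL2 | 4.1.1 as written | 6.6.1 |
|---|---|---|
| Grade 4 neutropenia or thrombocytopenia, 7 days or less | DLT | not a DLT |
| Febrile neutropenia, 2 days or less | DLT | not a DLT |
| Grade 2 or 3 anaemia | DLT | not a DLT |
| Grade 2 non-haematologic event, other than the ALT/AST-with-bilirubin criterion | DLT | not a DLT |
| Grade 3 event on the 6.6.1 exclusion list (eg nausea controlled within 3 days) | DLT | not a DLT |
| Most other non-haematologic events of grade 3 or more | DLT | DLT |

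Grade 3 IRR is left out of the table. Section 6.6.1 is itself unclear on it: the general grade 3 rule does not exclude it, but the only IRR named is grade 4.

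**Step 2: which text is intended.**

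- The trigger list in 4.1.1 has a separate DLT item that cites 6.6.1. It would be redundant if the other triggers were already DLTs.
- Section 4.1.2.3 sets two distinct conditions for deciding on two evaluable subjects: no non-haematologic toxicity of grade 2 or more (with an allowance for low-grade IRRs), "nor any DLT during the 28-day DLT period".
- Section 6.6.1 applies its own criteria to all AEs in the window.
- Section 6.6.2 allows treatment to continue once a DLT has recovered to grade 2 or less, which makes little sense for a DLT that was never above grade 2.
- The classification sentence fits its place in the Note to 6.6.1, where the specified grades are those of 6.6.1. In 4.1.1 it looks carried over.

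**Step 3: the plan's decision boundaries.** Section 4.1.2 gives φ = 0.30, φ1 = 0.6 × 0.30 = 0.18 and φ2 = 1.4 × 0.30 = 0.42.

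- Escalate at or below ln[(1−φ1)/(1−φ)] / ln[φ(1−φ1)/(φ1(1−φ))] = ln(0.82/0.70) / ln(0.246/0.126) = 0.2365.
- De-escalate at or above ln[(1−φ)/(1−φ2)] / ln[φ2(1−φ)/(φ(1−φ2))] = ln(0.70/0.58) / ln(0.294/0.174) = 0.3585.

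These are the stated 24% and 36%, and every cell of Table 4-3 follows from them and the termination rule in 4.1.2.2.

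**Step 4: one trigger-only event.** Suppose one subject has grade 4 neutropenia for 5 days. The level expands to three under either text, because the event is a trigger in both. The other two subjects are clean.

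- Under 6.6.1: 0/3 = 0, below 0.2365, so escalate.
- Under 4.1.1: 1/3 = 0.333, between the boundaries, so remain and treat a further cohort. With three more clean subjects: 1/6 = 0.167, below 0.2365, so escalate.

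The figure that 4.1.1 puts in the report therefore depends on dosing. It is 1/3 if dosing followed 6.6.1 and only the tabulation followed 4.1.1, and 1/6 in this example if dosing followed 4.1.1 as well. Under 6.6.1 it is 0/3.

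**Step 5: the DDS.** Suppose the same subject also missed a Cycle 1 dose. The subject is in the DDS only if the event is a DLT, so the first three subjects give 1/3 under 4.1.1 and 0/2 under 6.6.1.

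**Step 6: no trigger-only event.** Both texts give the same count.

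**The case against.** The strongest reply is that the documents already resolve the clash. Section 6.6.1 is the dedicated DLT section, it covers every AE in the window, and 4.1.1 itself points to it. On this view the sentence is an editorial leftover and not a rival definition. That stands as to intent and is why the point is minor. It does not make the sentence harmless, because it is worded as an instruction to classify and nothing in the SAP overrides it.

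A second reply is that the matter is largely past, and this too mostly stands. The two levels concerned are 0.2 to 0.6 mg/kg and 2 mg/kg. Sections 4.3.2 and 4.3.3 already fix the RP2D at 16 mg/kg. The DLT window is 28 days, so later follow-up cannot add DLTs at completed levels. SAP 1.2 places the primary escalation analysis together with the RP2D declaration. What remains is any RRMM escalation reporting still to come, including the final addendum.

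A reader might instead infer a deliberate, stricter DLT definition for the first two levels. The separate DLT trigger and Section 4.1.2.3 speak against that, and no passage announces such a rule.

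**Conclusion.** The contradiction is real. Section 4.1.1 as written counts three classes of event that 6.6.1 does not: haematologic events of grade 2 or more below the 6.6.1 thresholds, grade 2 non-haematologic events other than the ALT/AST-with-bilirubin criterion, and grade 3 events that 6.6.1 expressly excludes. Section 6.6.1 should govern.

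The size is small and conditional. It assumes that a trigger-only event occurred at MM-DL1 or MM-DL2 and that someone applied 4.1.1 literally; the documents show neither. Severity: minor.

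Two stronger readings are tempting. One is that the dose escalation, and with it the 16 mg/kg RP2D, is in doubt. The documents do not support this: the RP2D was chosen on all available escalation data, and the sentence reaches only the two lowest levels. The other is that the DLT rate for the whole RRMM escalation is materially inflated. The plan summarises escalation data by dose level and indication and specifies neither a pooled RRMM DLT rate nor a confidence interval for DLT incidence, so there is no planned figure of that kind to be wrong.

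**What to change.** - In SAP 4.5, state that a DLT is an event meeting the criteria of protocol Section 6.6.1, and that an event which only triggered expansion under 4.1.1 is not one. Refer to this from SAP 5.3 and 5.5.2.2. Apply it to any RRMM Dose Escalation reporting still to come, including the final addendum.
- At the next protocol amendment, delete the classification sentence from 4.1.1 and keep the statement that these AEs are relevant for expanding from one to three subjects. Do not write a separate DLT definition for the single-subject levels.

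The cost is one SAP sentence, two cross-references and one deletion. The SAP is still based on protocol version 5.0 while the protocol is at version 8.0, so a SAP update is a natural place for it. The deletion does not need an amendment of its own. No new data are needed and no past decision is reopened.

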#### Subjects with R/R AML

The R/R AML Cohort will be initiated after the trial has cleared the DL of 16 mg/kg in the RRMM Cohort with preliminary data on safety, PK, and pharmacodynamics in RRMM subjects who have been treated with GEN3014 at DLs up to 16 mg/kg (see Section 4.3.1.2). See Table 4-2 for further details on dosing schedule.

**Table 4-2 GEN3014 Dose Administration – Subjects with R/R AML (Dose Escalation)**

Subjects with AML	Minimum Number of Subjects	Dose Level	Dose Administered in Cycle 1	Dose Administered Each Dosing Day, Cycle 2 and Beyond
CCI				

**Note:** For AML-DL cohorts, split doses are administered on Days 1-2 of Cycle 1; full doses are administered on subsequent dosing days.

Additional DLs or modified dosing schedule(s) may also be explored based upon emerging data.

AML=acute myeloid leukemia; DL=dose level; R/R AML=relapsed or refractory acute myeloid leukemia.

In the R/R AML Cohort, in the Dose Escalation, the default DL size will be 3 subjects, from the start. Based on emerging data in subjects with AML treated with GEN3014, DLs for AML including intermediate doses will be adjusted accordingly during the course of the trial.

#### All DL Cohorts (RRMM and R/R AML)

After all subjects within a DL have completed the DLT evaluation period, the DEC will evaluate all available data (including but not limited to safety, PK, pharmacodynamic, and immunogenicity data) and propose initiation of the next DL. The Safety Committee will have to endorse the proposal before the next DL can start enrolling subjects. To supplement the routine safety monitoring by the Safety Committee as outlined in this protocol, a DMC will monitor safety data for the trial on a quarterly basis or more frequently as determined by the sponsor. Additional details regarding the DEC, Safety Committee, and the DMC can be found in Section 10.1.7.

The timeframe for administering the first dose to subjects at a specific DL should proceed as follows:

- For an investigated, non-cleared DL, there should be at least 3 days between administration of the first dose to the first subject and the second subject within the same DL.
- Any additional subjects enrolled in the investigated, non-cleared DL should receive the first dose at least 1 day apart.
- For a DL cleared for safety as recommended by the DEC/Safety Committee, there is no specific time frame for receiving the first dose among subjects (ie, additional subjects may be treated in parallel at the respective DL that are considered safe).

#### **4.1.1.1 GEN3014 Administration Schedule for Dose Escalation**

GEN3014 will be administered as an IV infusion in cycles of 4 weeks, ie, 28 days, as follows:

- Cycle 1: Days 1, 2, 8, 15, and 22 (Q1W) – see [Table 4-1](#) and [Table 4-2](#). Note that for RRMM, MM-DL1 will also have dosing on Day 9.
- Cycle 2: Days 1, 8, 15, and 22 (Q1W)
- Cycle 3-6: Days 1 and 15 (Q2W)
- Cycle 7 and beyond: Day 1 (Q4W)
- Each infusion is estimated to last between 1 and 8 hours. Please refer to the investigational medicinal product (IMP) manual for GEN3014 infusion guidelines.

Pre-infusion medication (corticosteroids, antipyretics, antihistamines, a leukotriene receptor antagonist) and post-infusion medication (corticosteroids) will be given as described in [Section 6.2](#) to reduce the risk of IRRs.

Note: Additional dosing schedules may be explored based on emerging data.

#### **4.1.1.2 Post-infusion Monitoring After GEN3014 Administration**

During treatment Cycle 1 in the Dose Escalation, subjects in the first 2 dose levels (MM-DL1 and MM-DL2) are required to remain in the clinic for at least 8 hours after each GEN3014 infusion so that they can be observed closely. During treatment Cycle 1, all other subjects are required to remain in the clinic after each GEN3014 infusion for at least 4 hours where they will be observed closely. Beyond observation for AEs, vital signs will be measured and blood sampling for laboratory parameters, cytokines, PK and pharmacodynamic measurements will be performed.

If clinically indicated, observation of up to 24 hours postdose during Cycle 1 is acceptable at the discretion of the investigator.

If a subject has an IRR of  $\geq$  grade 3 during any infusion, the subject will be required to stay overnight following the infusion. If a subject is hospitalized for prolonged monitoring post-infusion, the hospitalization should not be reported as serious adverse events (SAEs).

#### **4.1.2 Escalation Model**

An mBOIN design will be utilized to make optimal recommendations at end of each observed cohort ([Liu and Yuan, 2015](#)). The target DLT rate is set to  $\phi = 30\%$  with the assumptions that  $\phi_1 = 0.6\phi$  is the highest sub-therapeutic DLT rate and  $\phi_2 = 1.4\phi$  is the lowest DLT rate that has excessive toxicity. Under these assumptions, the observed DLT rates that rule if the next DL should be an escalation or de-escalation from the current DL are 24% and 36%, respectively ([Liu and Yuan, 2015](#)).

The DLT rate for a DL is estimated as total number of DLTs/total number of subjects treated (at that level). Based on the accrued data (on each DL) the mBOIN decision rules are supplied in [Table 4-3](#). [Section 9.2.1](#) presents simulations of the number of dosed subjects under different DLT rates.

For the AML escalation the target toxicity rate is set to  $\phi = 25\%$ . With similar definitions of what is the sub-therapeutic DLT rate, and what constitutes the lowest DLT rate that has excessive toxicity, the mBOIN decision rules are supplied in [Table 4-4](#). For cohort sizes of 3 DLT evaluable subjects, the BOIN rule is modified to follow 3+3 run-in design.

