**Table 4-3 Modified BOIN Decision Rules**

	Total Number of Subjects Treated at a Dose Level	2	3	4	5	6	7	8	9
Decision Based on Total Number of DLTs at the Dose Level	Escalate	0	0	0	$\leq 1$	$\leq 1$	$\leq 1$	$\leq 1$	$\leq 2$
	Remain	-	1	1	-	2	2	2	3
	De-escalate	1	2	2	2	3	3	3	4
	Terminate a dose level	$\geq 2$	3	$\geq 3$	$\geq 3$	$\geq 4$	$\geq 4$	$\geq 4$	$\geq 5$

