#### **4.1.2.2 Dose Level Termination**

A potential drawback of the basic BOIN design is that, theoretically, a very toxic DL could be investigated in multiple DLs, if a neighboring DL is not toxic. To avoid this problem, a DL termination criterion is implemented as a modification to the basic BOIN: A certain DL can no longer be investigated if an additional DLT-free cohort would lead to de-escalation. All higher DLs should also be terminated.

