## **9.3 Populations for Analyses**

**Full Analysis Set (FAS):** The FAS and safety set are defined in the same way and will comprise all enrolled subjects who receive at least 1 dose of trial drug (GEN3014 or daratumumab SC). In case of any deviations from planned dosing, subjects will be treated as per actual dosing.

The FAS will be used to summarize efficacy and safety analyses.

**Response Evaluable Set (RES):** Comprises all subjects in the FAS that at the timing of data cutoff date (for any interim reporting of the ongoing data):

- have measurable disease at baseline;
- had  $\geq 1$  on-treatment disease assessment;
- have died within 60 days of first trial treatment without post-baseline disease assessment (these are included as non-responders)

**Safety Set:** See definition for FAS.

**Per-Protocol Set:** Not applicable

**Dose-Determining Analysis Set (DDS):** The DDS will include all FAS subjects in the Dose Escalation part who meet the minimum exposure criterion and have sufficient safety evaluations or experience a DLT during the first 28 days of dosing (ie, in Cycle 1).

A subject will meet the minimum exposure criterion if the subject receives 4 out of the 4 preplanned doses during the DLT period. (The 2 initial split doses in Day 1 and Day 2 account for 1 preplanned dose.)

**Pharmacokinetic Analysis Set 1 (PAS1):** The PAS1 will include all enrolled subjects who receive at least 1 dose of trial drug (GEN3014 or daratumumab SC) and who provide at least 1 evaluable PK sample.

**Pharmacokinetic Analysis Set 2 (PAS2):** The PAS2 will include all enrolled subjects who received all 8 weekly GEN3014 or daratumumab SC doses in Cycles 1 and 2 with the cumulative dose administered amounting to 80% to 125% of the planned dose and provided a predose PK blood sample on Cycle 3 Day 1.

**Immunogenicity Analysis Set (IAS):** The IAS will include all enrolled subjects who receive at least 1 dose of trial drug (GEN3014 or daratumumab SC) and have a baseline and at least 1 evaluable on-treatment ADA sample.

**Biomarker Analysis Set (BAS):** The BAS will include all enrolled subjects who receive at least 1 dose of trial drug (GEN3014 or daratumumab SC) and have at least 1 evaluable biomarker sample.

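### The escalation rule divides DLTs by subjects treated, while the cohort rules and the dose-determining set use DLT-evaluable subjects; one non-evaluable subject can make the recommendation less cautious

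*Protocol*

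**What the plan says.** Protocol 4.1.2 sets a target DLT rate of 30% for RRMM and 25% for AML. It gives the rate to be compared with the boundaries as follows: "The DLT rate for a DL is estimated as total number of DLTs/total number of subjects treated (at that level". For RRMM, the observed rates that decide whether the next step "should be an escalation or de-escalation from the current DL are 24% and 36%, respectively". The columns of Table 4-3 are headed "Total Number of Subjects Treated at a Dose Level" and its rows "Decision Based on Total Number of DLTs at the Dose Level"; Table 4-4 for AML uses the same two headings. Section 4.1.2.2 adds the termination rule: "A certain DL can no longer be investigated if an additional DLT-free cohort would lead to de-escalation".

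Elsewhere the unit is the DLT-evaluable subject. Section 4.1.2.3 says that "each 3-subject cohort may consist of 2 to 4 subjects who are evaluable for DLT". It applies Table 4-3 to a level with three enrolled and two evaluable, where neither of the two had a DLT or a listed lower-grade toxicity: "In this example the BOIN would recommend an escalation", without replacing the third subject. It sends the reader to Section 9.3 for the definition of evaluable. The AML 3+3 run-in in 4.1.2 is likewise stated for evaluable subjects.

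Section 9.3 then says: "The DDS will include all FAS subjects in the Dose Escalation part who meet the minimum exposure criterion", with sufficient safety evaluations, or who have a DLT in the first 28 days. The exposure criterion is all four planned Cycle 1 doses. SAP 4.5 repeats this and excludes parallel-cohort subjects. SAP 5.3 presents DLTs on the DDS. Protocol 4.1.2.4, by contrast, brings every subject on an over-recruited level into the algorithm if it later de-escalates to that level.

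**The concern.** The rule that recommends the next dose level and the set that reports the primary DLT endpoint have different denominators, and the difference has a direction. Read as exposure plus safety data, or else a DLT, the DDS definition admits any main-cohort subject who has a DLT. A main-cohort subject left out is therefore DLT-free. Keeping that subject in the denominator can only pull the observed rate down.

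A site or committee following 4.1.2 and the table headings as printed could then get a less cautious recommendation than one following 4.1.2.3, from the same data. The DLT rates behind the dose decisions would also not match the DLT incidence in the report. Separately, a total number of DLTs can be read as events or as subjects with at least one. Section 6.6.1 lists several criteria that one subject could meet, and 6.6.2 foresees a second DLT episode in a subject.

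**Working it through.** **Reproducing the plan's boundaries.** Inputs from 4.1.2: φ = 0.30, φ1 = 0.6φ = 0.18, φ2 = 1.4φ = 0.42.

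- Escalation: ln[(1−φ1)/(1−φ)] / ln[φ(1−φ1)/(φ1(1−φ))] = ln(0.82/0.70) / ln(0.246/0.126) = 0.2365.
- De-escalation: ln[(1−φ)/(1−φ2)] / ln[φ2(1−φ)/(φ(1−φ2))] = ln(0.70/0.58) / ln(0.294/0.174) = 0.3585.

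These round to the stated 24% and 36%. With termination when x/(n+3) reaches the de-escalation boundary, every cell of Table 4-3 is reproduced. For AML (φ = 0.25) the boundaries are 0.1968 and 0.2984. Table 4-4 is reproduced except at 3 subjects with 1 DLT, where the documented 3+3 run-in applies.

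**One non-evaluable, DLT-free subject.** I looked up the same DLT count x at n treated and at n−1 evaluable, for n = 3 to 9 and x = 0 to n−1 (42 comparisons per table). Where Table 4-4 lists a count under both de-escalate and terminate, I took terminate.

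| Table | Treated / evaluable | DLTs | Treated count | Evaluable count |
|---|---|---|---|---|
| 4-3 (RRMM) | 3 / 2 | 1 | remain | de-escalate |
| 4-3 | 3 / 2 | 2 | de-escalate | terminate |
| 4-3 | 5 / 4 | 1 | escalate | remain |
| 4-3 | 6 / 5 | 2 | remain | de-escalate |
| 4-3 | 6 / 5 | 3 | de-escalate | terminate |
| 4-3 | 9 / 8 | 2 | escalate | remain |
| 4-3 | 9 / 8 | 3 | remain | de-escalate |
| 4-3 | 9 / 8 | 4 | de-escalate | terminate |
| 4-4 (AML) | 3 / 2 | 1 | remain | de-escalate |
| 4-4 | 4 / 3 | 2 | de-escalate | terminate |
| 4-4 | 6 / 5 | 1 | escalate | remain |
| 4-4 | 7 / 6 | 2 | remain | de-escalate |
| 4-4 | 8 / 7 | 3 | de-escalate | terminate |

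That is 8 of 42 in Table 4-3 and 5 of 42 in Table 4-4. In all 13 the treated count is the less cautious. With x = 0 there is no difference. As a check on rates: 1/5 = 20% lies below 23.65%, whereas 1/4 = 25% lies between the boundaries; 2/6 = 33.3% lies between them, whereas 2/5 = 40% exceeds 35.85%.

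**How often, given one non-evaluable subject.** For 6 treated and 5 evaluable in RRMM, the discrepant counts are 2 and 3.

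- True rate 30%: Binomial(5, 0.30) gives 0.309 + 0.132 = 0.441.
- True rate 10%: Binomial(5, 0.10) gives 0.073 + 0.008 = 0.081.

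For 9 treated and 8 evaluable the figures are 69% and 19%.

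**Events versus subjects.** If one affected subject has two DLTs, the event count is x+1 and the subject count x. At 3 RRMM subjects, 2 events gives de-escalate and 1 subject gives remain. At 5, 2 events gives de-escalate and 1 subject gives escalate. The two counts lead to different entries in 19 of 44 cells of Table 4-3 and 16 of 44 of Table 4-4.

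**The case against.** The strongest reply is that the intended denominator can be inferred. Section 4.1.2.3 uses Table 4-3 with evaluable subjects, the run-in is stated for them, the set is named dose-determining, and SAP 4.5 reasons from the algorithm to membership of that set. On this view, treated is loose wording. The inference is fair, but 4.1.2 defines the rate explicitly and both tables repeat the definition. A rule that yields a less cautious recommendation when followed literally should not depend on inference.

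Second, 4.3.2 and 4.3.3 record that 16 mg/kg has been selected as the RRMM RP2D, so new wording cannot affect that choice. This stands. No AML RP2D is stated, however, and 4.1.1 still allows additional dose levels.

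Third, table outputs are recommendations; the Dose Escalation Committee reviews all available data and the Safety Committee decides. This also stands and limits the consequence.

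Several stronger readings are tempting, and the documents do not support them:

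- **That the rule counts events, so a subject with two DLTs counts twice.** No text says so. A rate set against a 30% target, and the Prob(DLT) scenarios in Table 9-1, imply subjects. SAP 5.5.2.2 counts a subject once per SOC or PT in AE tables, which supports this without settling it. It is an ambiguity, not a shown error.
- **That non-evaluable subjects generally need no replacement.** Section 4.1.2.3 says this only for the two-of-three case free of DLTs and the listed toxicities, where both counts give escalate. The 3/2 rows above are weaker for that reason; the 5/4, 6/5 and 9/8 rows do not depend on it.
- **That a non-evaluable subject must have missed doses.** Such a subject may have had all four and lacked sufficient safety evaluations.

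**Conclusion.** The inconsistency is real and worth correcting. Followed as written, the treated denominator can give a less cautious recommendation than the evaluable denominator used in the protocol's own cohort rules and DDS. It can never give a more cautious one when the excluded subject is out for exposure or insufficient safety evaluations.

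The size is conditional. The 44% and 8% assume exactly one non-evaluable subject among six, independent subjects and the stated true rate. They include no probability that a subject is non-evaluable, and they ignore the path by which the level reached six. A reader might infer that one non-evaluable subject changes the decision, or that the RRMM dose selection is in doubt. The first overstates it: most table cells agree, and all agree with no DLTs. The second has no support, because the documents do not report any decision on which the two counts differed.

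What remains at stake is any further AML or additional dose-level decision, and agreement between the decision data and the reported DLT incidence. This review does not say which dose decision would be right in any cell.

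**What to change.** Reconcile Protocol 4.1.2, Tables 4-3 and 4-4, 4.1.2.3, 4.1.2.4 and 9.3 with SAP 4.5 on one numerator and one denominator. State in 4.1.2 and both table headings that the boundaries, unchanged, apply to the number of DLT-evaluable subjects with at least one DLT over the number of DLT-evaluable subjects, in line with 4.1.2.3 and 9.3.

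A bare reference to the DDS is not enough, because SAP 4.5 leaves out parallel-cohort subjects whom 4.1.2.4 brings in after de-escalation to an over-recruited level. State whether those subjects count as evaluable for the algorithm and whether they enter the reported DLT incidence.

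The cost is wording, with two consequences to accept knowingly. A level with a non-evaluable subject may get a more cautious recommendation or need one more subject. Counting subjects rather than events is less cautious than the literal event count when one subject has several DLTs.
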